### Accumulation Ratio

To investigate whether the dose of LT3001 drug product is accumulated in the 3-day TID regimen, the potential dose accumulation effect will be assessed by comparing PK parameters of the first dose and the last dose in the multi-day TID regimen of LT3001 drug product.

Using a linear mixed-effects model with Race, Day (Day 1, first dose and Day 3, last dose), and Race-by-Day interaction as fixed effects, and subject as a random effect on log-transformed data, the geometric means and corresponding 95% CIs for  $AUC_{0-t}$ ,  $AUC_{0-\tau}$ , and  $C_{max}$  will be presented for Chinese and Non-Asian subjects by exponentiating the model-based least-squared means. The geometric mean ratios (last dose/first dose) and the corresponding 90% CIs will also be calculated overall and for each race based on this model to assess accumulation.

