#### 4. Objectives and Endpoints

Objectives	Endpoints
Primary	
Part A 

To determine the safety, tolerability, and PK of a 3-day TID use of LT3001 drug product, when administered as an IV infusion q3h between each dose within one day in healthy subjects (with half Chinese population).

	Part A 

Nature and severity of adverse events (AEs) and number of subjects with AEs

Changes from baseline in physical examination, vital signs, electrocardiogram (ECG) assessment, oximetry, coagulation, and clinical laboratory tests.

Plasma PK parameters of LT3001

Urine PK parameters of LT3001

Effects of LT3001 drug product on systolic and diastolic blood pressure (SBP/DBP), prothrombin time (PT), activated partial thromboplastin time (aPTT), and thrombin time (TT)

Part B 

To determine the safety and PK of LT3001 when coadministered with aspirin, clopidogrel, apixaban or dabigatran

	Part B 

Nature and severity of AEs and number of subjects with AEs

Changes from baseline in physical examination, vital signs, ECG assessment, oximetry, platelet function test, coagulation, and clinical laboratory tests.

Plasma PK parameters of LT3001

Plasma PK parameters of aspirin, clopidogrel, apixaban and dabigatran

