#### Part A

Eligible subjects will be admitted to the site on Day -1 and undergo additional eligibility assessments. Those reconfirmed as eligible will be randomly assigned to study treatment. Approximately 16 healthy subjects will be randomized in a 3:1 ratio to receive either LT3001 drug product [REDACTED] or placebo administered as a 15-minute intravenous (IV) infusion. Each subject will receive three doses, administered 3 hours apart, on Days 1, 2, and 3. Subjects will be released from the site on Day 4 following all safety and PK procedures.

The first 4 subjects will be “sentinel subjects,” with 2 subjects assigned to receive LT3001 drug product and the other 2 subjects assigned to receive placebo. The Investigator will review all available safety data from the sentinel subjects. If considered safe to do so, the remaining subjects will be dosed.

The remaining subjects may not proceed to receive study drugs in the event of any of the following:

- A subject treated with LT3001 drug product experiences any hemorrhage which is assessed as related to LT3001 drug product
- A subject treated with LT3001 drug product experiences any SAE is assessed as related to LT3001 drug product (at least possibly related)
- Safety concerns per the Investigator's clinical judgment

The dosing schema is summarized below.

The safety observation period may be extended beyond Day 4 in the event of any signal of significant clinical concern raised by the Investigator.

It will require approximately 5 weeks for each subject to complete all the required study procedures of Part A, including screening period, and blood samples will be collected from each subject for safety and PK evaluation during the study. Duration of both inpatient stay and PK sampling may be subject to change, depending on emerging safety and PK results.

After all healthy subjects complete study procedures of Part A, the safety review meeting will be held by the Investigator and the sponsor medical monitor (or designee) to review all available safety and blood PK data of all subjects and determine whether one or more of the following should occur:

- Enrollment of subjects of Part B will proceed
- More subjects should be enrolled, up to a maximum of 16 subjects in LT3001 drug product group, based on safety and blood PK data
- Refinement of PK sampling times is recommended
- A protocol amendment is recommended

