**Figure 5 Dosing Schema of LT3001 and Dabigatran Co-administration**

**5.2. Participant and Study Completion**

Approximately 16 subjects (8 Chinese and 8 non-Asian) will be enrolled in Part A and 48 subjects in Part B. A subject will have completed the study when the final PK and safety assessments are done at the end-of-study (EOS) or follow-up visit.

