**5.4. Scientific Rationale for Study Design**

Studies comparing the PK and safety of a drug product in Chinese and non-Asian subjects allow for extrapolation of clinical data across regions. Use of healthy participants rather than patients minimizes confounding factors due to disease. Randomization and blinding minimizes bias in the assessment of safety and interpretation of results. The susceptibility of LT3001 to drug interaction will be assessed by measuring LT3001 when administered alone and in combination with aspirin, apixaban, clopidogrel, and dabigatran. Similarly, the effect of LT3001 on aspirin, apixaban, clopidogrel, and dabigatran will be assessed by measuring those analytes alone and in combination with LT3001.

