### **7.4. Method of Treatment Assignment**

In Part A, the first four sentinel subjects will be randomly assigned to LT3001 drug product or placebo in a 1:1 ratio. The remaining subjects will be randomized in a 3:1 ratio.

In Part B, subjects will be sequentially assigned to one of four treatment cohorts.

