### 6.4. Subgroup Analyses

Although no subgroup analyses are planned, Part A results will be presented by treatment (LT3001 and placebo) and population (Chinese and Non-Asian) and Part B results will be presented by cohort.

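### Part A: the SAP fits race in its PK model but asks for no confidence interval on the Chinese/non-Asian exposure ratio that protocol 5.4 gives as a design rationale

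*SAP*

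**What the plan says.** Protocol 5.4 opens with the reason for recruiting two populations: "Studies comparing the PK and safety of a drug product in Chinese and non-Asian subjects allow for extrapolation of clinical data across regions". Protocol 5.2 sets the numbers: "Approximately 16 subjects (8 Chinese and 8 non-Asian) will be enrolled in Part A and 48 subjects in Part B". The Part A objective (protocol 4) repeats that half the sample is to be Chinese, but lists no between-population comparison among its objectives or endpoints.

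SAP 6.4 states that no subgroup analyses are planned, but that "Part A results will be presented by treatment (LT3001 and placebo) and population (Chinese and Non-Asian"). SAP 8.2 summarises LT3001 concentrations descriptively by population.

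The one model for Part A PK is in SAP 8.2, Accumulation Ratio. It is a mixed model on log-transformed data, with race, day (first dose on Day 1, last dose on Day 3) and their interaction as fixed effects and subject as random. It has two outputs:

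- geometric means with 95% CIs for AUC0-t, AUC0-tau and Cmax, which "will be presented for Chinese and Non-Asian subjects by exponentiating the model-based least-squared means";
- last/first-dose geometric mean ratios with 90% CIs, overall and within each race, to assess accumulation.

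No Chinese/non-Asian ratio with an interval appears in SAP 6.4, SAP 8.2 or protocol 10.3.2.

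**The concern.** Neither output compares exposure between the populations with a measure of uncertainty. The last/first-dose ratios are within-population quantities. The race-by-day term addresses whether accumulation differs between populations, not whether exposure does.

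A reader who wants the comparison named in protocol 5.4 must set two intervals side by side. Overlap of two intervals is a more lenient standard for calling the groups similar than an interval for the ratio. A real difference could therefore pass as similarity, which is the wrong direction of error when the purpose is to carry data across regions. With so few subjects, the width of the ratio's interval is itself the main message, because it shows how little extrapolation the data can bear.

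**Working it through.** **Plan's own figure.** There is none to reproduce. Protocol 10.1 and SAP 4.1 say that sample size had no statistical basis, and the documents give no CV for LT3001.

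**Is the ratio available from the planned model?** Yes. With non-Asian and Day 1 as reference levels, the log ratio is the race coefficient at the Day 1 first dose, and race plus race-by-day at the Day 3 last dose. Exponentiating either one gives the geometric mean ratio.

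**Number on LT3001.** Protocol 5.1 says "Approximately 16 healthy subjects will be randomized in a 3:1 ratio to receive either LT3001 drug product" or placebo, which for 16 gives 12:4. Protocol 7.4 says "the first four sentinel subjects will be randomly assigned to LT3001 drug product or placebo in a 1:1 ratio", with the rest at 3:1, which gives (2 + 9):(2 + 3) = 11:5. The two do not agree, so 6 + 6 and 5 + 6 per population are both shown.

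**Expected 90% CI at one dose, true ratio 1.** The limits are exp(± t × s × √(1/n1 + 1/n2)), with s = √ln(1 + CV²), t the 95th percentile on n1 + n2 − 2 degrees of freedom, and CV assumed.

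For 6 + 6 at CV 30%: s = √ln(1.09) = 0.2936; SE = 0.2936 × √(1/6 + 1/6) = 0.1695; t on 10 df = 1.812; exp(1.812 × 0.1695) = 1.36; interval 0.74 to 1.36.

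| Assumed CV | 6 + 6 | 5 + 6 |
|---|---|---|
| 20% | 0.81-1.23 | 0.80-1.25 |
| 30% | 0.74-1.36 | 0.72-1.38 |
| 40% | 0.67-1.50 | 0.65-1.53 |

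The mixed model pools residual variance over two days, so its degrees of freedom may be somewhat higher and its intervals slightly narrower.

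**Two separate intervals against one interval for the ratio (n per group, same confidence level, same t).**

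- Separate intervals stop overlapping when |d| > 2 × t × s/√n.
- The ratio's interval excludes 1 when |d| > t × s × √(2/n).
- The quotient is 2/√2 = 1.41 on the log scale.

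Example at 95%, 6 + 6, CV 30%: t on 10 df = 2.228. The ratio's interval excludes 1 at exp(2.228 × 0.1695) = 1.46-fold. The separate intervals separate at exp(1.414 × 2.228 × 0.1695) = 1.71-fold.

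**Effect of population imbalance on the ratio (11 on LT3001).** The SE is proportional to √(1/n1 + 1/n2): 0.6055 for 5/6 and 0.6268 for 4/7. Then 0.6268/0.6055 = 1.035, an increase of 3.5%.

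**The case against.** The strongest reply is that the comparison was never promised. It is a sentence of rationale, not a listed objective or endpoint. SAP 6.3 says that no hypothesis testing is done, SAP 6.4 says that no subgroup analyses are planned, and descriptive reporting by population looks like a deliberate choice. SAP 2 also leaves room for unlisted exploratory analyses. Most of this stands, and it limits the weight of the point. It does not remove it: an exploratory interval is neither a test nor a new model, and SAP 8.3 already uses ratios with 90% CIs for every interaction in Part B.

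A second reply is that the populations do get estimates. That is correct: the point ratio follows from the two reported means, and only its interval is absent. Nor does the SAP tell anyone to judge by overlap; the 1.41 describes what happens if a reader does.

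A third reply is that an interval of 0.74-1.36 settles nothing. It cannot show similarity, and it should not be read that way. Its use is to make that limit visible.

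A reader might also infer that assignment is not stratified by population. The documents do not support that as a statement of fact. Protocol 7.4 and 7.5 name no population stratum, but the Part A allocation table is redacted in SAP 4 and missing after the schema sentence in protocol 5.1, so the split by population may be set there. If there were no stratification, a 4/7 split in place of 5/6 would cost the ratio little precision, as shown above.

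**Conclusion.** The point holds as a missing contrast with its interval, not as a missing population analysis. The design rationale names a comparison and the planned model can estimate it, but the SAP does not request the interval. It is a low-cost improvement to the plan and does not threaten a listed objective.

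The 1.41 factor assumes equal group sizes, a common variance and the same confidence level throughout. Setting the SAP's 95% intervals against a 90% CI for the ratio would give 1.41 × 2.228/1.812 = 1.74, but part of that is only the change of confidence level, so 1.41 is the fair figure. The expected widths rest on CVs of 20% to 40% that are assumed, and on 5 or 6 LT3001 subjects per population. The stronger readings, that the populations go without any estimate or that randomisation ignores population, go beyond what the visible text shows.

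**What to change.** In SAP 8.2, Accumulation Ratio, add that the model already specified will also report the Chinese/Non-Asian geometric mean ratio with 90% CI for AUC0-t, AUC0-tau and Cmax, at the Day 1 first dose and at the Day 3 last dose. Label it exploratory estimation and state that no equivalence conclusion will be drawn.

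The cost is one contrast statement per time point and one table row per parameter and time point. It needs no new data, model or subjects, and it applies whatever the redacted allocation table contains.

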### 8.3. Plasma PK: Part B

#### Plasma PK Concentration

Plasma concentrations of LT3001, aspirin (and metabolite salicylic acid), clopidogrel (and metabolite clopidogrel acid), apixaban, and dabigatran will be summarized by cohort with descriptive statistics: n, mean, SD, CV%, geometric mean, geometric CV%, median, minimum, and maximum.

Plots of mean (SD) plasma concentration by time will be presented for LT3001 and concomitant medications by cohort in linear and semi-logarithmic scales as well.

Plasma concentrations of LT3001, concomitant medications, and metabolites for concomitant medications (Part B, Cohorts 1 and 2) at each nominal timepoint will be listed by subject.

#### Plasma PK Parameters

The following plasma PK parameters will be calculated for Part B for LT3001, concomitant medications, and metabolites for concomitant medications (Part B, Cohorts 1 and 2):

- $C_{max}$ : Maximum (peak) plasma drug concentration during a dosing interval
- $C_{min}$ : Trough plasma concentration
- $C_{av}$ : Mean steady-state drug concentration
- $t_{max}$ : Time to reach the observed maximum (peak) plasma concentration
- $\lambda_z$ : Apparent first-order terminal elimination rate constant, calculated by linear least-squares regression analysis on the terminal log-linear phase of the plasma concentration vs time curves using at least 3 time points
- $AUC_{0-t}$ : Area under the plasma concentration-time curve from time zero to the time of last quantifiable concentration, calculated by the linear trapezoidal linear interpolation method
- $AUC_{0-\tau}$ : Area under the plasma concentration-time curve over the dosing interval  $\tau$  at steady-state
- $R_{acc}$ : Accumulation ratio calculated as  $AUC_{0-\tau, 1st\ dose}/AUC_{0-\tau, last\ dose}$  for the multi-day LT3001 regimens
- $MRT_{0-\infty}$ : Mean residence time, calculated as  $[AUMC_{0-\tau} + \tau(AUC_{0-\infty} - AUC_{0-\tau})]/AUC_{0-\tau} - (TI/2)$  where  $AUMC_{0-\tau}$  is the area under the moment curve over dosing interval  $\tau$  and  $TI$  represents infusion duration
- $t_{1/2, \lambda}$ : Elimination half-life, calculated as  $0.693 / \lambda_z$
- $CL$ : Total body clearance of the drug from plasma, calculated as Dose /  $AUC_{0-\tau}$

- $V_z$ : Apparent volume of distribution during the terminal phase, calculated as (Dose /  $AUC_{0-\tau} / \lambda_z$ )

All calculations for PK parameters will be based on actual dosing and sampling times recorded during the study. Plasma and urine pharmacokinetic parameters will be summarized (n, arithmetic mean, SD, CV%, minimum, median, and maximum) and listed by subject. Geometric mean (GM) and geometric CV% will also be presented for all AUC,  $C_{max}$ ,  $C_{av}$ , and  $C_{min}$ .

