## **7.10. Treatment Compliance**

LT3001 drug product will be administered via an IV infusion by the Investigator or qualified personnel. Aspirin, clopidogrel, dabigatran, and apixaban will be orally administered under the direct supervision of the Investigator or designee. A hand and mouth check will be done to ensure that the medication was swallowed.

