#### Plasma PK Parameters

The following plasma PK parameters will be calculated for Part A for LT3001:

- $C_{\max}$ : Maximum (peak) plasma drug concentration during a dosing interval
- $C_{\min}$ : Trough plasma concentration
- $C_{av}$ : Mean steady-state drug concentration
- $t_{\max}$ : Time to reach the observed maximum (peak) plasma concentration

- $\lambda_z$ : Apparent first-order terminal elimination rate constant, calculated by linear least-squares regression analysis on the terminal log-linear phase of the plasma concentration vs time curves using at least 3 timepoints
- $AUC_{0-\infty}$ : Area under the plasma concentration-time curve from time zero to infinity, calculated as  $AUC_{0-t} + C_t / \lambda_z$ , where  $C_t$  is the last measurable concentration
- $AUC_{0-t}$ : Area under the plasma concentration-time curve from time zero to the time of last quantifiable concentration, calculated by the linear trapezoidal linear interpolation method
- $AUC_{0-\tau}$ : Area under the plasma concentration-time curve over the dosing interval  $\tau$  at steady-state
- $R_{acc}$ : Accumulation ratio calculated as  $AUC_{0-\tau, 1st\ dose}/AUC_{0-\tau, last\ dose}$  for the multi-day LT3001 regimens
- $MRT_{0-\infty}$ : Mean residence time, calculated as  $[AUMC_{0-\tau} + \tau(AUC_{0-\infty} - AUC_{0-\tau})]/AUC_{0-\tau} - (TI/2)$  where  $AUMC_{0-\tau}$  is the area under the moment curve over dosing interval  $\tau$  and  $TI$  represents infusion duration
- $t_{1/2, \lambda}$ : Elimination half-life, calculated as  $0.693 / \lambda_z$
- $CL$ : Total body clearance of the drug from plasma, calculated as  $Dose / AUC_{0-\infty}$
- $V_z$ : Apparent volume of distribution during the terminal phase, calculated as  $(Dose / AUC_{0-\infty}) / \lambda_z$
- $V_{ss}$ : Apparent volume of distribution during steady state, calculated as  $CL \times MRT$

All calculations for plasma PK parameters will be based on actual dosing and sampling times recorded during the study. Plasma and urine pharmacokinetic parameters will be summarized (n, arithmetic mean, SD, CV%, minimum, median, and maximum) and listed by subject. Geometric mean (GM) and geometric CV% will also be presented for all AUC,  $C_{max}$ ,  $C_{av}$ , and  $C_{min}$ .

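### SAP 8.3 applies one set of intravenous steady-state formulas for CL, Vz and MRT to every Part B analyte and dose, and omits the AUC0-∞ that other Part B analyses need

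*SAP*

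**What the plan says.** The Part B list in SAP 8.3 (Plasma PK Parameters) opens: "The following plasma PK parameters will be calculated for Part B for LT3001, concomitant medications, and metabolites for concomitant medications", the metabolites being those of Cohorts 1 and 2. The same section names them as salicylic acid and clopidogrel acid. Only the accumulation ratio is limited, to the multi-day LT3001 regimens. The relevant entries are:

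- AUC0-τ: "Area under the plasma concentration-time curve over the dosing interval" τ, at steady state.
- CL: "Total body clearance of the drug from plasma, calculated as Dose", with AUC0-τ as the denominator.
- Vz: the same ratio divided by λz, named as an apparent volume.
- MRT: [AUMC0-τ + τ(AUC0-∞ − AUC0-τ)] / AUC0-τ − TI/2, where TI "represents infusion duration".

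AUC0-∞ is not in this list. Protocol 9.4 and SAP 8.2 (Part A) do list it, and both define CL as Dose/AUC0-∞.

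On route, Protocol 7.10 states: "Aspirin, clopidogrel, dabigatran, and apixaban will be orally administered". LT3001 is given as a single 15-minute infusion on Day 1 of each cohort. It is then given three times daily, 3 h apart, for three days starting on Day 6, 7, 5 and 5 in Cohorts 1 to 4 (SAP 4).

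**The concern.** The formulas suit an intravenous drug at steady state. The Part B list applies them to three situations where that does not hold: oral dosing, metabolites that are formed rather than given, and LT3001 doses with no preceding regimen. It also leaves out an AUC that the same section uses elsewhere.

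Plasma PK parameters of LT3001 and the four partner drugs are Part B endpoints (Protocol 4, SAP 3.2), and SAP 8.3 says that they will be summarised and listed. Followed literally, the tables would show oral clearances under the wrong name and metabolite clearances with no defined meaning. LT3001 first-dose clearance would be defined differently in Part A and Part B.

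**Working it through.** The plan states no numerical result for CL, Vz or MRT, so there is none to reproduce. The check takes each analyte and occasion in turn. Half-lives for LT3001, bioavailability F and absorption rate ka are not readable in the documents; the values used for them are assumptions.

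**1. Oral parents (aspirin, clopidogrel, apixaban, dabigatran).** At steady state F·Dose = CL·AUC0-τ, so Dose/AUC0-τ = CL/F, and dividing by λz gives Vz/F. Read as CL, the value is too high by 1/F: 1.11 times at F = 0.9, 2 times at 0.5, 4 times at 0.25.

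Steady state is a fair premise for the two anticoagulants. SAP 4 claims 97% for apixaban and 94% for dabigatran after three days. At the slow end of the stated half-lives, 1 − 2^(−72/14) = 97.2% and 1 − 2^(−72/17) = 94.7%, so both claims reproduce.

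For MRT there is no infusion, so TI = 0. The formula then returns disposition MRT plus mean absorption time. With an assumed half-life of 12 h and ka = 0.3/h, this is 12/0.693 + 1/0.3 = 17.3 + 3.3 = 20.6 h, against 17.3 h for disposition alone.

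**2. Metabolites.** The numerator of CL and Vz is a dose, and neither metabolite is dosed. Without the fraction of parent converted and a molar conversion, neither of which is in the plan, CL and Vz are undefined. MRT would mix the parent's absorption and conversion with the metabolite's own residence.

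**3. LT3001 doses not at steady state.** Day 1 is a single dose. The first combination dose follows four to six days later, so it is also a first-dose profile. For one compartment, with k = ln2/t½, TI = 0.25 h and τ = 3 h, the share of AUC0-∞ beyond τ is

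q = (1 − e^(−k·TI)) · e^(−k(τ − TI)) / (k·TI),

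and Dose/AUC0-τ exceeds Dose/AUC0-∞ by the factor 1/(1 − q).

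| Assumed t½ | k·TI | q | CL overstated by |
|---|---|---|---|
| 0.25 h | 0.693 | 0.500 × 2^(−11) / 0.693 = 0.00035 | 0.04% |
| 0.5 h | 0.347 | 0.293 × 2^(−5.5) / 0.347 = 0.0187 | 1.9% |
| 1 h | 0.173 | 0.159 × 2^(−2.75) / 0.173 = 0.136 | 15.8% |

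Vz shifts by the same factor. Against AUMC0-∞/AUC0-∞ − TI/2, the MRT formula is off by 0%, 0.3% and 1.4% in the same three cases. A slow phase would matter more: with a 0.25 h main phase and 10% of the initial coefficient in a 1 h or 3 h phase, the CL factor is 1.04 or 1.42.

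**4. Last LT3001 dose.** It is the third infusion of the day. Ignoring carry-over from the day before, its AUC over 3 h equals the single-dose AUC from 0 to 9 h. At t½ = 1 h the missing share is 0.159 × 2^(−8.75) / 0.173 = 0.002, so Dose/AUC0-τ with τ = 3 h is adequate there.

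**5. AUC0-∞.** The MRT formula contains it. SAP 8.3 also names it among the LT3001 geometric mean ratio parameters for apixaban and dabigatran; the aspirin and clopidogrel paragraphs use AUC0-τ in that place. Section 8.3 therefore uses a parameter that its own list does not call for.

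**The case against.** The best defence is that little goes numerically wrong.

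- For the oral parents the calculation is right at steady state, Vz is already called apparent, and TI = 0 removes the infusion term. This stands: the fault there is the CL label and the missing /F.
- Protocol 9.2 says that LT3001 has a short half-life and that no accumulation is expected. The Cohort 2 sampling schedule in SAP 4.2, as far as it can be read, ends about 60 minutes after the start of infusion. Both point to the low end of the table. This also stands, but no half-life is given to settle it.
- The protocol determines parameters as far as the data allow and as appropriate. That leaves room to skip a meaningless metabolite value but does not correct the definition. SAP 8.3 has no such qualifier, and SAP 2 says that its methods amend or supersede the protocol's.

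Three stronger readings are tempting, and the documents do not support them:

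- A reader might infer that six of the seven Part B analytes get wrong values. For the four oral parents, CL and Vz are valid once named CL/F and Vz/F. Only the two metabolites lack a dose, and they are not in the endpoint lists of Protocol 4 or SAP 3.2.
- A reader might infer that LT3001 clearance cannot be compared between Day 1 and the combination days. The interaction models compare Day 1 with the first combination dose. Both are first-dose profiles under the same formula, so the truncation largely cancels.
- A reader might infer that interaction conclusions are at risk through these parameters. The accumulation and interaction models in SAP 8.3 use AUC, Cmax and, for LT3001, trough concentration; CL, Vz and MRT do not enter them.

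**Conclusion.** The point holds as a fault of definition and labelling, with minor consequences. As written, SAP 8.3 mislabels clearance for four oral drugs and requests undefined CL and Vz for two metabolites. It uses a steady-state AUC for LT3001 doses that are not at steady state, and omits AUC0-∞ although the section relies on it. The first two do not depend on any assumed value.

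The size of the LT3001 discrepancy does. It is 0.04% to 1.9% for one compartment with half-lives of 0.25 to 0.5 h, and 15.8% at 1 h, a value that no passage supports. The 50–200% and 80–125% assessments do not change through CL, Vz or MRT.

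**What to change.** In SAP 8.3, split the Part B list by analyte and occasion:

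- **All of Part B:** add AUC0-∞ to the list, with the SAP 8.2 definition.
- **LT3001, Day 1 and first combination dose (Day 6, 7, 5 and 5 in Cohorts 1 to 4):** CL = Dose/AUC0-∞ and Vz = CL/λz. Both occasions must change together; changing Day 1 alone would create a mismatch in the interaction contrast.
- **LT3001, last dose:** CL = Dose/AUC0-τ, with τ stated as 3 h.
- **Oral parents:** report CL/F and Vz/F. Compute MRT without the TI/2 term, with a note that it includes absorption time.
- **Salicylic acid and clopidogrel acid:** omit CL, Vz and MRT.

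The cost is SAP wording, table and listing labels, and one derivation (AUC0-∞ in Part B). No new samples or visits are needed. AUC0-∞ relies on extrapolation with λz, so the extrapolated share should be listed beside it.
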